We hypothesize that administration of TXA will reduce perioperative bleeding in osteotomy procedure with minimal side effects. As a result, swelling and postoperative pain will decrease thus improving postoperative outcomes. While TXA has been used in various orthopedic surgeries to reduce bleeding, no study has investigated the efficacy of TXA during a TTO procedure and TXA during HTOs have limited available studies. The available literature shows perioperative bleeding and hematoma significantly decreased during HTO procedures³. By comparing high tibial osteotomy patients to tibial tubercle osteotomy patients, we will determine if there is a difference in efficacy or if both cohorts will be similarly affected.

Study Design

This is a single-center, prospective cohort study. Patients will be assigned to their cohorts based on diagnosis and appropriate treatment as determined by the surgeon. Patients will be consented in the study once they are scheduled for either a HTO or TTO, therefore this will not be a randomized study. The study is comparing blood loss and postoperative pain after TXA administration in patients receiving a high tibial osteotomy (HTO) to patients receiving a tibial tubercle osteotomy (TTO) with or without medial patello-femoral ligament (MPFL) reconstruction. One gram of intravenous tranexamic acid will be administered before tourniquet inflation and 1 gram of IV TXA before closure of the incision. Patients will be asked on postoperative day 1, 2 and 7 to rate their pain according to the VAS scale. Patients will have their knee swelling measured immediately postoperatively and at their one-week follow up visit. The swelling ratio is defined as the postoperative mean circumference of upper pole of patella and lower pole of patella divided by the preoperative values.

Primary Objective

The primary objective of the study is to determine if there are any differences in blood loss between patients undergoing high tibial osteotomy (HTO) and tibial tubercle osteotomy (TTO) with or without medial patello-femoral ligament (MPFL) reconstruction.

Secondary Objective

Secondary objective of the study is to determine if there is a difference in post operative pain and swelling between patients undergoing HTO compared to patients undergoing TTO.

II. CHARACTERISTICS OF THE RESEARCH POPULATION

Number of Subjects

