The total number of subjects enrolled will be approximately forty (40) patients, with 20 patients in the HTO cohort and 20 patients in the TTO cohort, calculated by post hoc analysis. The Patients will be recruited from routine clinical practice at The NYU Langone Health, Langone Orthopedic Hospital, Sports Medicine Division.

Gender of Subjects

Men and women will be included in this study.

Age of Subjects

Subjects included study will be at least 18 years of age.

Racial and Ethnic Origin

There are no enrollment restrictions based on race or ethnic origin.

Inclusion Criteria

Patients will be screened for eligibility using the following criteria. All study subjects must meet the following inclusion criteria:

- Patients undergoing a high tibial osteotomy (HTO)
- Patients undergoing tibial tubercle osteotomy (TTO) with or without medial patello-femoral ligament (MPFL) reconstruction
- Patients ages 18-60, inclusive

Exclusion Criteria

Patients meeting the following criteria will be excluded from participation in this study:

- Legally incompetent or mentally impaired (e.g., minors, Alzheimer's subjects, dementia, etc.)
- Younger than 18 years of age
- Older than 60 years of age
- Any patient considered a vulnerable subject including: pregnant women or fetuses, children, cognitively impaired adults, prisoners
- history of coagulation abnormalities and thromboembolic disease or current abnormal coagulation test values
- history of stroke or acute coronary syndromes within 3 months before surgery
- Preoperative (chronic) anticoagulation therapy
- Abnormal coagulation profile
- Renal failure (serum creatinine $> 250 \mu\text{mol/L}$ [2.83 mg/dL]) or liver cirrhosis
- Sickle cell disease
- Patients with a history of hypersensitivity to Percocet and/or TXA

Vulnerable Subjects

We do not intend to enroll vulnerable subjects.

Subject withdrawal criteria. Patients are free to withdraw at any time from the study.

III. METHODS AND PROCEDURES

Methods and Procedures

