Data monitoring will be done by [name], the principal investigator. He will review the following accumulated data quarterly.

He will monitor whether or not:

1. Collection and storage of patient data was performed in a sensitive and secure manner, as defined in the informed consent form and protocol, ensuring information is stored on REDCap.
2. All study activities were conducted with primary emphasis on patient care and wellbeing, ensuring the patients are not in discomfort and have an abnormally high VAS following the surgery.
3. If there were any adverse events, and if so were addressed appropriately and per protocol
4. The risk/benefit to patients has remained the same throughout the course of the study.

The study will be stopped if there are unexpected severe AE's in more than one patient. Adverse events will be defined as negative reactions to the intravenous TXA during or after surgery, including seizures, vision problems. We will submit summaries of data and safety monitoring annually.

Data Analysis

According to a post hoc power analysis calculating the effect size using our preliminary data, >15 patients are required with $d=0.6$ to obtain a power of 0.80 and an alpha value of 0.05. Therefore we are including an additional 5 patients per group to account for patients that may be

lost to follow up. Statistical analysis will be performed using chi-squared and/or fisher's exact testing depending on size for binary variables. Continuous variables will be compared with paired t-tests if the data is approximately normally distributed. If the data is not normally distributed, Mann-Whitney tests will be used. All protected health information will be removed prior to statistical analysis. We will use patient subjective pain, perioperative blood loss and knee swelling data as statistical endpoints. Subjective pain will be measured with the VAS (visual analogue scale), perioperative blood loss will be measured looking at blood loss from the suction drain after surgery. The swelling ratio is defined as the postoperative mean circumference of upper pole of patella and lower pole of patella divided by the preoperative values according to our previous study. The endpoints must be statistically significant between the two cohorts to show TXA is effective.

Data Storage and Confidentiality

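### The sample-size statement does not reproduce: d = 0.6 at 80% power needs 45 patients per cohort, and the planned 20 give about 46% power

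*Combined protocol and SAP*

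**What the plan says.** The only sample-size justification is in section III, Data Analysis. From preliminary data it concludes that ">15 patients are required with $d=0.6$ to obtain a power of 0.80 and an alpha value of 0.05". It continues: "Therefore we are including an additional 5 patients per group to account for patients that may be" lost to follow-up. Section II, Number of Subjects, gives the resulting enrolment as "20 patients in the HTO cohort and 20 patients in the TTO cohort, calculated by post hoc analysis".

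The comparison is between different patients. Under Study Design, "Patients will be assigned to their cohorts based on diagnosis and appropriate treatment as determined by the surgeon", and the Primary Objective asks whether blood loss differs in any way between HTO and TTO patients. Data Analysis names paired t-tests for continuous variables, with Mann-Whitney tests if the data are not normal.

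The plan does not state whether alpha is one- or two-sided, which endpoint d refers to, or the mean difference and SD behind it.

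**The concern.** Fifteen per group is far too few to detect a 0.6 SD difference between independent groups with 80% power. Two groups of that size reach 80% only for an effect of about one SD, so n and d do not belong to the same calculation.

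The error affects how the result is read. Data Analysis makes statistical significance between the cohorts the criterion for its conclusion, and the Rationale intends to say whether the two procedures are similarly affected. A reader who believes the study had 80% power at d = 0.6 could take a non-significant result as good evidence against a difference of that size. With the planned numbers and a two-sided test, non-significance is the more likely outcome even when that difference is real.

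The calculation is also called post hoc, although it is used to set future enrolment.

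**Working it through.** **Inputs**

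- d = 0.6, power 0.80, alpha 0.05: Data Analysis.
- n = 15 per group before the loss allowance: Data Analysis gives more than 15 and adds 5 per group, and Number of Subjects gives 20 per cohort. Since 15 + 5 = 20, the working figure is 15.
- Two independent groups, 1:1: Study Design and Number of Subjects.
- Two-sided test: an assumption, taken from the non-directional Primary Objective. One-sided results are also shown.

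**Step 1. Try to reproduce the plan's figure**

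Normal approximation for two independent means:

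n per group = 2 × ((z₀.₉₇₅ + z₀.₈₀) / d)² = 2 × ((1.96 + 0.8416) / 0.6)² = 2 × 21.80 = 43.6, so 44.

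The exact noncentral-t calculation gives 44.6, so **45 per group, 90 in total**. The stated 15 is one third of that.

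**Step 2. Try other readings**

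| Reading (d = 0.6, 80% power, alpha 0.05) | n needed | Power at n = 15 | Power at n = 20 |
|---|---|---|---|
| Independent t, two-sided | 45 per group | 35.5% | 45.6% |
| Independent t, one-sided | 36 per group | 48.3% | 58.7% |
| Paired t, two-sided | 24 pairs | 58.0% | 72.1% |
| Paired t, one-sided | 19 pairs | 71.4% | 82.7% |

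- Mann-Whitney, two-sided, at relative efficiency 0.955: 45 / 0.955 = 47.1, so 48 per group.
- If 0.6 were Cohen's f (d = 1.2): 12 per group.
- If more than 15 is read as 16 per group: two-sided independent power is 37.6%.
- If 15 were the total for both groups, power would be lower still.

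No reading gives 15. If the figure is taken as 16, the nearest is a one-sided paired normal approximation: ((1.645 + 0.8416) / 0.6)² = 17.2, so 18. That design does not apply to two unrelated cohorts.

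**Step 3. Power of the planned numbers at d = 0.6 (independent, two-sided)**

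Noncentrality = d × √(n/2), with 2n − 2 degrees of freedom.

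- n = 20: 0.6 × √10 = 1.90, 38 df, critical t 2.024, power 45.6%.
- n = 15: 0.6 × √7.5 = 1.64, 28 df, critical t 2.048, power 35.5%.

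**Step 4. Effect detectable with 80% power (independent, two-sided)**

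- 20 per group: d = 0.91.
- 15 per group: d = 1.06.

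**Step 5. Precision**

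Approximate half-width of the 95% confidence interval for the difference, in SD units: t × √(2/n).

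- 20 per group: 2.024 × √(2/20) = 0.64 SD.
- 15 per group: 2.048 × √(2/15) = 0.75 SD.

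**The case against.** The arithmetic is not in dispute. The best case on the other side concerns how far it reaches.

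- **Sidedness is not stated.** With a one-sided test and all 20 per cohort evaluable, power is 59%, so a true 0.6 SD difference would be found more often than missed. This stands as a condition: the statement that such a difference is more likely missed than found at 20 per cohort assumes a two-sided test. At 15 per cohort it holds either way (35% and 48%). Neither version reaches 80%.
- **The plan names a paired test.** Twenty pairs tested one-sided would have 83% power, and a paired formula may be where the error began. This does not rescue the plan. The design has no pairing, the objective is non-directional, the 20 already contains the loss allowance, and 15 pairs still fall short.
- **Late loss matters less for the primary endpoint.** Blood loss is read from the suction container at surgery, so loss before the one-week visit should not usually remove it. That stands. About 46% is the relevant figure for blood loss, and 35% applies mainly to day-7 pain and swelling if all five allowed losses occur.
- **The mistake may be in d rather than n.** Fifteen per group fits d of about 1.06, and the documents do not show which number is misreported. This also stands, and it is why the correction should give both power at 0.6 and the detectable effect.
- **Post hoc may only mean that d came from preliminary data.** That is plausible. The source of d should stay in the text, but the label is wrong for a calculation that sets enrolment.

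**Conclusion.** The concern holds and must be fixed. For the unpaired comparison that the protocol describes, tested two-sided at 0.05, d = 0.6 needs 45 evaluable patients per cohort for 80% power. The planned 20 give about 46%, falling to about 35% if only 15 are evaluable. The effects detectable with 80% power are 0.91 SD and 1.06 SD.

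The exact percentages rest on a two-sided test, equal groups, and approximately normal outcomes with a common SD. The finding that 15 is wrong does not depend on sidedness or pairing, because all four t-test readings need more. Whether n or d was misreported cannot be settled from the documents.

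**What to change.** Enrolment can stay as planned. In section III, Data Analysis, and section II, Number of Subjects:

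1. Check the preliminary data. Name the endpoint behind d and give its mean difference and SD. If d was misreported, correct it.
2. Replace the power statement with one such as: *Twenty evaluable patients per cohort give 46% power for d = 0.6 and 80% power for d = 0.91; fifteen per cohort give 35% power and 80% power for d = 1.06 (unpaired t-test, two-sided alpha 0.05).*
3. Remove the post hoc label in both sections, but keep the statement that d was estimated from preliminary data.
4. Change the paired t-test sentence to an unpaired test in the same edit, so that the power statement and the analysis agree.
5. Report the HTO–TTO difference with its 95% confidence interval (expected half-width about 0.64 SD at 20 per cohort), and say that a non-significant result will not be read as showing similarity.

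The cost is a small text edit and a less favourable stated power, with no added patients. If the sponsor prefers to keep 80% power at d = 0.6, the requirement is 45 evaluable per cohort. With the plan's own loss allowance (5/20 = 25%), that means enrolling 45 / 0.75 = 60 per cohort.

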Patients indicated and scheduled for a high tibial osteotomy or tibial tubercle osteotomy with or without medial patello-femoral ligament reconstruction will be identified from faculty surgeon case logs at the NYU Langone Health, Langone Orthopedic Hospital Sports Medicine Division. After informed consent is obtained, a chart review of patients' medications and past medical histories will be reviewed based on their electronic medical records to identify any current pain medications or exclusion criteria. Patients will be in the study for 1 week, until their first follow up visit.

Patients will be given 1 gram of intravenous tranexamic acid (TXA) before tourniquet inflation and 1 gram of IV TXA before closure of the incision. Immediate post-operative management will not be affected by this study. The study team will not be blinded to the study as there is no randomization to each cohort. All patients will receive a standardized regimen of aspirin for DVT prophylaxis and Percocet for pain management, which is standard of care post-operative treatment.

Information to be recorded pre-operatively includes age, sex, height, weight, BMI, and American Society of Anesthesiology (ASA) classification. Intra-operative information will also be recorded, including operative time, and estimated blood loss. During the surgery, a suction device is utilized to remove excess blood from the surgical site and sucked into the suction drain and placed into a measuring cup. We will measure the perioperative blood loss by look at the measuring cup and seeing how much blood is inside. Knee swelling postoperatively will be measured using the swelling ratio. The swelling ratio was defined as the circumference of the operative limb divided by the circumference of the contralateral limb. Pain severity scores at rest will be assessed by use of a visual analog scale (VAS; 0 = no pain, 10 = worst pain imaginable) at 0.5, 1, 1.5, 2, 4, 6, 24, and 48 hours as well as 7 days after surgery. Percocet consumption will be recorded at 24 hours, 1 day, 2 days and 7 days after surgery. Incidence of TXA-related side effects (nausea/vomiting, itching, anxiety, increased thirst, rapid heartbeat) in the first 24 hours will be noted. Time to discharge from the post-anesthesia care unit (PACU) and time to discharge from the hospital will be recorded.

Analysis and Data Monitoring

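### Paired t-tests are specified for comparing two separate, unmatched cohorts, so in the normal-data branch the primary p-value depends on how HTO patients happen to be lined up with TTO patients

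*Combined protocol and SAP*

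**What the plan says.** For continuous endpoints, Data Analysis (section III) gives two branches. The first is "Continuous variables will be compared with paired t-tests if the data is approximately normally distributed". The second is "If the data is not normally distributed, Mann-Whitney tests will be used". The same section lists pain, perioperative blood loss and knee swelling as endpoints, and sets the criterion for success: "The endpoints must be statistically significant between the two cohorts to show TXA is effective".

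The comparison is between different people. Under Study Design (section I), "Patients will be assigned to their cohorts based on diagnosis and appropriate treatment as determined by the surgeon", and the study is not randomised. The primary objective compares blood loss in HTO patients with blood loss in TTO patients, and the secondary objective does the same for pain and swelling. Number of Subjects (section II) plans 20 patients in each cohort. No section describes matching or a rule for pairing one patient with another.

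**The concern.** A paired t-test analyses differences within natural pairs, such as two measurements on one patient or two matched patients. Here an HTO patient and a TTO patient have nothing to link them. To run the test, the analyst must line up the two columns in some order, and the protocol gives none. The order of rows in the data file would then decide the p-value for the primary endpoint.

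Three things follow:

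- The result is not reproducible, because two analysts with the same data could report different p-values.
- The order could be chosen after seeing the outcomes. No pairing rule is fixed in advance, and Methods and Procedures says the study team is not blinded.
- If the cohorts end up unequal in size, the test cannot be run without discarding evaluable patients.

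The two branches also assume different designs. The non-parametric counterpart of a paired t-test is the Wilcoxon signed-rank test, not Mann-Whitney. As written, a check of normality would switch the analysis from paired to independent samples.

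**Working it through.** **1. Could any pairing be intended?** Taking the endpoints in turn:

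- *Blood loss:* one reading per patient. Methods and Procedures says "We will measure the perioperative blood loss by look at the measuring cup and seeing how much blood is inside", with no baseline or second value.
- *Swelling:* each definition given is a ratio, so two circumferences already become one number per patient.
- *Pain (VAS):* measured repeatedly, but no analysis of change over time is stated, and the objective is HTO versus TTO.

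No within-patient reading rescues the text for the comparisons that the plan makes.

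**2. Does the sample size imply a paired design?** The plan states that ">15 patients are required with $d=0.6$ to obtain a power of 0.80 and an alpha value of 0.05", then adds 5 per group, giving 20. Exact calculations at d = 0.6, power 0.80 and two-sided alpha 0.05 give 45 per group for an independent t-test. For a paired t-test, with 0.6 read as the standardised mean difference within pairs, they give 24 pairs. One-sided, the figures are 36 per group and 19 pairs. None reproduces 15 or 16, so the sample size does not show that pairing was intended. The shortfall itself is a separate matter.

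**3. Why the p-value moves.** With n per cohort, mean difference D and standard deviations s₁ and s₂:

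- Independent test: t = D / √(s₁²/n + s₂²/n), on 2n − 2 = 38 df (pooled, equal n).
- Paired test: t = D / √[(s₁² + s₂² − 2·r·s₁·s₂)/n], on n − 1 = 19 df.

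Here r is the sample correlation created by the chosen row order. D, s₁ and s₂ do not depend on the order; r does. For unrelated patients r is noise, with standard deviation 1/√(n − 1) = 1/√19 = 0.229 over random pairings.

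**4. Example at an observed d of 0.6** (s₁ = s₂ = 1, n = 20):

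- Independent: t = 0.6/√(2/20) = 1.897, p = 0.065. There is only one answer.
- Paired, r = 0: t is again 1.897, but on 19 df p = 0.073.
- Paired, r = +0.45 (1.96 × 0.229): t = 0.6/√(1.10/20) = 2.558, p = 0.019.
- Paired, r = −0.45: t = 0.6/√(2.90/20) = 1.576, p = 0.13.
- The critical value on 19 df is 2.093, so p < 0.05 needs r > 1 − 10 × (0.6/2.093)² = 0.178. That is 0.178/0.229 = 0.78 standard deviations, or about 22% of pairings.

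A simulation of 20,000 random pairings of one such data set agrees: median p 0.073, central 95% range 0.019 to 0.131, full range 0.0016 to 0.170, and 22.6% below 0.05. Pairing the same values in rank order gives p = 1.7 × 10⁻⁹; reverse rank order gives 0.19.

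**5. Example at the boundary.** In a simulated data set with an unpaired p of 0.050, 10,000 random pairings gave paired p-values with median 0.057 and central 95% range 0.015 to 0.107; 39% were below 0.05. The formula agrees. The unpaired t is 2.024, so p < 0.05 needs r > 1 − (2.024/2.093)² = 0.065, or 0.28 standard deviations, which is about 39% of pairings.

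**6. Average behaviour over many trials** (20 per cohort, normal data):

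| | Paired, arbitrary order | Independent |
|---|---|---|
| Type I error | about 0.05 | about 0.05 |
| Power at d = 0.6 | 0.437 | 0.456 |

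The two tests reach different decisions in about 7% of trials at d = 0.6 and about 2% at d = 0. If values were paired in sorted order, type I error would be 0.60.

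**7. Unequal cohorts.** As an illustration, with 20 and 16 evaluable patients the paired test can use 16 pairs and drops 20 − 16 = 4 patients.

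**The case against.** The best defence is that *paired* is a slip for *unpaired*. Mann-Whitney is the natural partner of an independent t-test, and the section speaks throughout of groups and cohorts. That is probably what was meant, but it does not remove the problem. The sentence is the governing text, nothing elsewhere corrects it, and an analyst who follows it runs the wrong test.

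Four limits on the size of the concern do stand:

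- It bites only if the data are judged approximately normal. Otherwise the plan already names a suitable independent-samples test.
- Pairing fixed without regard to outcome keeps type I error at its nominal level, and costs only about 2 percentage points of power.
- The 39% figure comes from a data set placed at the decision boundary. In most data sets the order changes the p-value but not the conclusion.
- Blood loss is read at surgery, so loss to follow-up would mainly unbalance the day-7 outcomes rather than the primary endpoint. The 20-versus-16 split is illustrative and does not come from the plan.

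**Conclusion.** The concern holds. The only parametric test named for the primary endpoint does not fit the design. There are no pairs, and the fallback test assumes the independent samples that the study actually has.

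The main harm is a primary p-value that is not unique and that could be steered by the choice of row order. Average loss of power is small (0.437 against 0.456 at d = 0.6), and error control survives only if the pairing is blind to outcome, which the plan does not secure.

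The numerical examples assume normal data with equal variances and 20 patients per cohort, because the documents give no mean or standard deviation for blood loss. Other data would change the ranges. The dependence on pairing follows from the formula and would remain.

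**What to change.** In Data Analysis, replace the paired t-test with an independent-samples t-test for every HTO-versus-TTO comparison of a continuous variable, and keep Mann-Whitney as its non-parametric counterpart. Welch's version is a sensible default because it does not assume equal variances; the pooled version would also cure the defect. If any within-patient change is to be analysed, such as pain over time, name it separately and reserve paired methods for it.

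The change is a few words, best made before any outcome data are analysed. It needs no new data, patients or procedures.

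### The Data Analysis success rule spans pain, blood loss and swelling, although only blood loss is primary, and the stated 0.80 is not the power of that rule

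*Combined protocol and SAP*

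**What the plan says.** Section I ranks the aims under separate headings. Under Primary Objective: "The primary objective of the study is to determine if there are any differences in blood loss between patients" having the two operations, HTO and TTO. Under Secondary Objective come postoperative pain and swelling.

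Data Analysis (section III) does not repeat that ranking. It says "We will use patient subjective pain, perioperative blood loss and knee swelling data as statistical endpoints", describes how each is measured, and closes with the decision rule: "The endpoints must be statistically significant between the two cohorts to show TXA is effective". It names no primary endpoint, testing order or multiplicity rule.

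The sample-size sentence in the same section opens "According to a post hoc power analysis calculating the effect size using our preliminary data". It requires more than 15 patients at d = 0.6 "to obtain a power of 0.80 and an alpha value of 0.05", and 5 per group are then added for loss to follow-up. Number of Subjects gives 20 HTO and 20 TTO patients. The endpoint behind d = 0.6 is not named, and neither the sidedness of the test nor any correlation between endpoints is given.

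Methods and Procedures lists nine VAS assessments, and Study Design lists two swelling measurements. No time point is selected for the decision rule.

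**The concern.** An endpoint that must be significant before the conclusion can be drawn is not acting as a secondary endpoint. An analyst who follows the objectives would judge the study on blood loss. One who follows Data Analysis would need blood loss, pain and swelling together. The same data could pass under one section and fail under the other, and the study team is unblinded, so the choice should not be left until results are seen.

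The power statement does not settle the matter. A single d, alpha and power describe a single comparison. If the conclusion needs three significant results, its power is a joint probability, which is lower than the power of each test unless the tests are perfectly correlated. A reader would then take 0.80 as the chance of a positive study when it is not.

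**Working it through.** **Inputs.** From Data Analysis: d = 0.6, alpha 0.05, power 0.80, more than 15 patients (read as per group, because 5 per group are added to reach 20). From Number of Subjects: 20 per group. Assumptions: two-sided tests; unpaired tests, because the cohorts are different patients (the plan's words are paired t-tests or Mann-Whitney); one test per endpoint; a common correlation ρ between the three test statistics, oriented in the direction of the true effects.

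**Step 1: the plan's own figure, one test.** For two independent means, n per group = 2(z₀.₉₇₅ + z₀.₈₀)²/d² = 2(1.960 + 0.842)²/0.36 = 43.6, so 44 (45 with the t distribution). The stated figure of just over 15 is not reproduced. A two-sided paired calculation does not give it either (24 pairs). With the noncentral t distribution, for one unpaired test:

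| n per group | power at d = 0.6 | d detectable with 0.80 power |
|---|---|---|
| 15 | 0.35 | 1.06 |
| 20 | 0.46 | 0.91 |

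**Step 2: the effect of the rule alone.** To keep the sample-size error out, grant each test a true power of 0.80. Then

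P(all three) = ∫ [Φ((z₀.₈₀ + √ρ·u)/√(1 − ρ))]³ φ(u) du,

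which at ρ = 0 is 0.80³ = 0.512.

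| ρ | all three significant, each test at 0.80 | all three, each test at 0.456 (n = 20, d = 0.6 on every endpoint) |
|---|---|---|
| 0 | 0.51 | 0.09 |
| 0.3 | 0.57 | 0.16 |
| 0.5 | 0.61 | 0.21 |
| 0.8 | 0.69 | 0.30 |
| 1 | 0.80 | 0.46 |

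The middle column is the effect of the rule. The right-hand column combines the rule with the sample-size error. At ρ = 0.5, the rule alone takes 0.80 to 0.61, the sample size alone takes 0.80 to 0.46, and both together give 0.21.

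**Step 3: type I error.** If all three must be significant, a false claim needs at least one true null to be rejected alongside the others, so the error cannot exceed 0.05. If any one is enough and there is no true difference, the error at ρ = 0 is 1 − 0.95³ = 0.143. It is about 0.125 at ρ = 0.5 and 0.098 at ρ = 0.8.

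**Step 4: number of tests.** Requiring significance at more than one of the listed VAS or swelling times could only lower the joint power in Step 2. Allowing any of those times to count could only raise the *any* error in Step 3.

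**The case against.** The strongest reply is that the protocol does have a hierarchy. Section I ranks the aims under explicit headings, and Data Analysis never calls the three endpoints co-primary. A reader might infer that the plan has three unranked, co-equal endpoints. The documents do not support that: neither the label used in Data Analysis nor the order of its list cancels the ranking in section I. What remains is narrower, namely that the decision sentence needs significance on endpoints that section I makes secondary.

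A reader might also infer an inflated false-positive rate. The sentence says that the endpoints must be significant, which plainly means all of them, and that reading costs power but does not inflate type I error. The 0.10–0.14 belongs only to the *any* reading, which the text does not exclude but does not favour.

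A third tempting step is to quote the joint power of 0.09 to 0.30 as the cost of the rule. It is not, because much of that shortfall comes from the sample size and would affect blood loss alone.

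It is also fair to object that the decision sentence has a more basic fault: both cohorts receive TXA, so a difference between HTO and TTO cannot show that TXA works. That is a separate defect. A rewrite could cure it and still leave pain and swelling in the success criterion.

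**Conclusion.** The point holds in limited form. The decision sentence in Data Analysis conflicts with the objectives in section I, and the stated 0.80 is not the power of the rule as written. On the plain *all* reading, the rule by itself lowers 0.80 to about 0.51–0.69 for correlations between 0 and 0.8. The direction is certain, since joint power equals 0.80 only at correlation 1. The size depends on assumed correlations and on one test per endpoint.

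Restoring blood loss as the only deciding endpoint would not rescue the 0.80. At d = 0.6, one unpaired two-sided test has power 0.46 with 20 per group and 0.35 with 15. That is a distinct error, and it must be corrected in the same edit.

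**What to change.** In Data Analysis:

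- Name blood loss as the sole primary endpoint, compared between HTO and TTO at two-sided 0.05.
- Restate the power for that one test and do not carry 0.80 over. With 20 per group it is about 0.46 at d = 0.6; equivalently, 0.80 power is reached for d of about 0.91. At d = 0.6, 0.80 would need about 45 per group.
- Report pain and swelling as secondary, with 95% confidence intervals and no claim of success.
- Replace the plural rule with a statement about the HTO–TTO difference in blood loss. The inference to TXA efficacy in that sentence needs its own correction.

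The edit is a few sentences and needs no new data. Its costs are that pain and swelling can no longer carry the conclusion and that the stated power becomes less favourable. Keeping all three as joint requirements would be dearer: by the Step 2 formula, joint power of 0.80 at d = 0.6 on each endpoint needs about 67, 62 or 56 per group at correlations 0, 0.5 and 0.8, before dropout.
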